Subjects who miss one to two days of the daily dose will continue at their present dose. Those who miss 3 to 4 days of the daily dose of study product will receive their next dose at the Allergy and Immunology Clinic and be observed for a minimum of 2 hours after dosing to assure safety with dosing. Those who miss more than 4 days will return to the Allergy and Immunology Clinic for a graded challenge. The subject will switch to a peanut equivalent dose once he/she reaches the maintenance dose or highest dose achieved.

The dosing guidelines for peanut flour will continue to be followed.

Table 1. Schedule during build-up phase for missed daily doses (time intervals from missed doses)
• Up to 2 days, continue doses as scheduled.
• 3-4 consecutive days after missed dose; repeat previous doses but dose will be given in the Allergy/Immunology Clinic.
• More than 4 days after missed dose, patient will return to Allergy/Immunology Clinic for a graded challenge.

6.3. Entry Oral Food Challenge (approximately 9 hours):

- Amount of blood to be drawn at this visit: Blood drawn to check the peanut-specific IgE, IgG and IgG4 levels, and cellular immune studies and basophil activation studies will be drawn and evaluated at Texas Children’s Center for Human Immunobiology (Baylor College of Medicine) for analysis.

IgG and IgG4 are antibodies that may have a role in tolerating peanut. They will be followed throughout the study and we will evaluate how they are changing while the subject is on therapy. In addition we will be obtaining blood for the immune cell studies.

- In order to obtain sufficient quantity of cells we will collect the maximum amount of blood allowable as defined by Texas Children’s Hospital based on the subject’s weight. This will range from 4 to 6 tablespoons total of blood drawn for the visit.
- Spirometry: Spirometry results or peak flow measures will be accepted. For participants that complete peak flow the results must be > 90% of predicted. For participants that complete spirometry, FEV1 must be greater than 90% predicted on the day of the challenge to participate in the food challenge.
- Targeted History and Physical Exam and Diet History: A brief medical and diet history will be obtained and a focused physical exam will be performed.

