dose (Table 4). The first dose of the peanut equivalent will be given in the hospital setting. The family will be instructed on how to administer peanut equivalent dose. The subject will continue to follow the “Instructions for Daily Home Doses” as used for peanut flour dosing. This will be considered “Month 0”. The participant will remain on this dose for 24 months and follow-up visits will occur every 6 months. The subject will continue to follow the peanut flour dosing guidelines. A food challenge will be performed within 1 month of the “Month 0” visit.

Table 4. Peanut Equivalent Dose

Peanut Product	Peanut Protein (gram) /serving	Maintenance Dose (3900mg peanut protein)	Alternative Dose (if maintaining below 3900mg)
Creamy Peanut Butter *Peter Pan or Reese’s Creamy Peanut Butter*	8 grams=2 Tablespoons	1 Tablespoon	1300 mg =1 teaspoon 325mg=0.25 teaspoon
JIF Peanut Powder	8 grams=3 Tablespoons	1.5 Tablespoons	
PB2 Powdered Peanut Butter (Bell Plantation)	5 grams=2 Tablespoons	1.5 Tablespoons	1300 mg= 1.5 teaspoon 300 mg = 3/8ths of a teaspoon
Dry Roasted Peanuts	0.175 grams=1 peanut	22 peanuts	1300 mg = 7 and ½ peanuts 350 mg = 2 peanuts
Peanut M&M’s	0.15 grams=1 piece	26 pieces	1300 mg = 8 and 2/3 pieces 300 mg=2 pieces
Reese’s Pieces Candy	0.078 grams=1 piece	50 pieces	1300 mg = 16 and 2/3 pieces 312 mg = 4 pieces
Reese’s Peanut Butter Cups Miniatures	0.8 grams=1 miniature cup	~5 miniature cups	1300 mg = 1 and 5/8 th cups 300 mg = 3/8 th cup

Other approved alternative:			
-----------------------------	--	--	--

- If the subject experiences no adverse events with the maintenance dose or highest dose tolerated after 1 month, the provider will have the option of decreasing the observation period at home to 1 hour. The subject will need to avoid any form of physical activity 2 hours after ingestion.
- Peak Flow: Peak flow measures will be accepted with results >90% of predicted.
- Amount of blood to be drawn: After maximum tolerated dose is achieved at approximately 1 year (drawn at Visit 30- Month 0 DBPCFC) and every 6 months afterwards, we will draw up to 4-6 tablespoons of blood (based on the subject's weight) for peanut-specific IgE, IgG, and IgG4, cellular immune studies and basophil histamine release assays until the end of the protocol.
- Allergy Skin Prick Tests (PST): Endpoint dilution skin testing to peanut will be done at month 0 and month 12 visits.

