- Targeted History and Physical Exam and Diet History: A brief medical and diet history will be obtained and a focused physical exam will be performed.
- Epinephrine injector will be checked for expiration date and parent/guardian will demonstrate proper use.
- Review Home Symptom Diary: At each visit we will review any symptoms experienced while taking the food protein.
- Administer Peanut Equivalent Dose: The first dose of the peanut equivalent will be given in the hospital setting followed by a 2 hour observation period.
- Urine Pregnancy Test: For females of reproductive potential a urine pregnancy test will be performed at month 0 and month 12 visits. If the subject is pregnant she will be dismissed from the study.

6.6. 0 Month Maintenance Study Food Challenge Visit (approximately 9 hours)

- The food challenge will need to be completed within 1 month of the "Month 0" visit.
- Amount of blood to be drawn: At this visit, we will draw up to 4-6 tablespoons of blood (based on the subject's weight) for peanut-specific IgE, IgG, and IgG4 and cellular immune studies, and basophil histamine release assays
- Spirometry or Peak Flow: Spirometry will be attempted in all participants. If valid spirometry results are not successfully obtained, the attempt is documented and peak flow measures will be accepted for the entry criteria with results >90% of predicted. For participants that are able to complete spirometry, FEV1 must be greater than 90% predicted on the day of the challenge to participate in the food challenge.

- Targeted History and Physical Exam and Diet History: A brief medical and diet history will be obtained and a focused physical exam will be performed.
- DBPCFC: The subject will come to Texas Children's Hospital in Houston for a Double Blind Placebo Controlled Food Challenge (DBPCFC) to the study protein (peanut) to determine if he or she is still allergic to peanut or can tolerate peanut.

The DBPCFC visit will last approximately 9 hours. The food challenge may be performed in one day or split into two days. The subject will discontinue antihistamines (for example Zyrtec or Claritin) for 7 days before the procedure and must be off oral corticosteroids for one month before the food challenge.

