Peanut equivalent will be used for the food challenge at 0 month maintenance food challenge. The challenge will consist of increasing doses of peanut (in the form of peanut equivalent) given every 15 minutes in increasing amounts (Table 5). The other challenge will consist of placebo material given also in increasing doses. The highest dose will be equivalent to approximately 34 peanuts.

- Review Home Symptom Diary: We will review any symptoms experienced while taking the food protein.
- Urine Pregnancy Test: For females of reproductive potential a urine pregnancy test will be performed prior to the food challenge. If the subject is pregnant the food challenge will not be performed and the subject will be dismissed from the study.

Table 5

0 Month Maintenance Phase Double-Blinded Placebo Controlled Food Challenge Protocol		
Dose Number	Approximate Dose Amount (PEANUT PROTEIN)	Cumulative Dose Amount (peanut protein)
1	75 mg	75 mg
2	150 mg	225 mg
3	500 mg	725 mg
4	1000 mg	1725 mg
5	2000 mg	3725 mg
6	3000 mg	6725 mg
7	4000 mg	10725 mg
8	4500 mg	15225 mg
9	5000 mg	20225 mg
10	6000 mg	26225 mg

6.7. End of Study Food Challenge Visits (24 and 25 months after maintenance dose is reached) (approximately 8 hours per visit):

- Amount of blood to be drawn: At both visits, we will draw up to 4-6 tablespoons of blood (based on the subject's weight) for peanut-specific IgE, IgG, and IgG4, cellular immune studies, and basophil histamine release assays
- Allergy Skin Prick Tests (PST): Endpoint dilution skin testing to peanut will be done at the month 24 and month 25 visit.
- Spirometry or Peak Flow: Spirometry will be attempted in all participants. If valid spirometry results are not successfully obtained, the attempt is documented and peak flow measures will be accepted for the entry criteria with results >90% of predicted. For participants that are able to complete spirometry, FEV1 must be greater than 90% predicted on the day of the challenge to participate in the food challenge.
- Targeted History and Physical Exam and Diet History: A brief medical and diet history will be obtained and a focused physical exam will be performed.
- DBPCFC: The subject will come to Texas Children's Hospital in Houston for a Double Blind Placebo Controlled Food Challenge (DBPCFC) to the study protein (peanut) to determine if he or she is still allergic to peanut or can tolerate peanut.

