6.9 Unscheduled Visit

Subjects may return to the site at any time throughout the study duration at the provider's discretion for additional evaluation if there are concerns of an adverse reaction. The procedures performed at unscheduled visits may include any or all of those performed at the build-up visits as well as spirometry. The procedures performed will be at the provider's discretion.

6.10 Scientific Rationale for Immune Cell Response Studies:

Peanut allergy has more than tripled in prevalence over the past decade, and there are no reliable predictors of peanut allergic reactions. This provides the impetus to conduct research to characterize the mechanistic factors driving the immune responses and evaluate the effect of T and NK T lymphocyte phenotypic and functional profiles in the development of tolerance to

peanut. A novel experimental polyfunctional flow cytometric method will be utilized. This research will address major deficiencies in the current knowledge regarding the effect of T and NK T lymphocyte activation and cytokine production in peanut allergic populations.

This approach will help elucidate the complex immune mechanisms involved in the expression of allergic inflammation in vivo in anaphylaxis. T cells are recognized to play a key role in the inhibition of adaptive immune responses through regulatory mechanisms in food allergic disease. Hence, a better characterization of surface and intracellular Th1, Th2, NKT and T regulatory responses will elucidate mechanistic pathways for maintenance of homeostasis.

Furthermore, the blood samples collected will be used to perform basophil histamine release assays in order to analyze basophil activation in the participants undergoing OIT. Recent studies have suggested that basophil activation was positively correlated with DBPCFC severity scores and that testing could discriminate between allergic and non-allergic subjects, thus serving as an additional tool to predict clinical severity.(22)

The specific aim is to define the role of peanut specific T cell responses on the regulation of tolerance in peanut allergic disease. The relationship between the level of tolerance (i.e. highest clinically tolerated peanut protein dose) and peanut specific T cell activation markers, transcription factors and intracellular inflammatory cytokine production will be further characterized. Furthermore, we will analyze basophil activation in subjects undergoing OIT.

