For Females of Reproductive Potential

Being a part of this study while pregnant may expose the unborn child to significant risks, some of which may be currently unforeseeable.

Other Risks

There may possibly be other side effects that are unknown at this time.

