8. DATA MANAGEMENT ISSUES

8.1. Sources of Research Material:

8.1.1. Existing records:

Previous CAP-FEIA serum IgE reports will be included in each subject's record. Existing subject medical records will not otherwise be used unless records are needed to verify or clarify the severity of the original reaction to peanut ingestion.

8.1.2. Data collected during research:

- Consent and assent
- Demographic information (age, sex, ethnicity)
- History and Physical examination (including diet history, family history, past medical and past surgical history)
- Allergy skin prick testing to peanut
- Mechanistic blood draws
- Serum Beta HCG and urine pregnancy test for all menstruating females.
- Observed dosing adverse event log.
- Concomitant medication administration while on study.
- Spirometry and/or peak flow
- Double-Blinded Placebo Controlled Food Challenge (DBPCFC) (for those with confirmed CAP-FEIA serum IgE > 7 and a negative pregnancy test).

8.1.3. Home diaries:

Symptom diaries will be recorded daily by participants.

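### No pregnancy test is scheduled during build-up (Visits 3 to 28), although pregnancy is an exclusion and, at later tests, a ground for dismissal

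*Combined protocol and SAP*

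**What the plan says.** Pregnancy is an exclusion (3.2), and girls of childbearing potential must be willing to use birth control for the whole study (3.1). Section 7 adds: "Being a part of this study while pregnant may expose the unborn child to significant risks, some of which may be currently unforeseeable".

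Tests are placed as follows.

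- **Screening (6.1, Visit 1):** a serum test for girls who are menstruating.
- **Build-up (6.4, Visits 3 to 28):** none. The section lists blood draws, peak flow, skin testing, history and examination, diary review, the injector check and dose escalation. The schedule's pregnancy-test row is blank there.
- **Maintenance (6.5):** "a urine pregnancy test will be performed at month 0 and month 12 visits". The consequence is "If the subject is pregnant she will be dismissed from the study".
- **Month 0 food challenge (6.6, Visit 30):** "a urine pregnancy test will be performed prior to the food challenge". The end-of-study challenges at Months 24 and 25 (6.7) have the same requirement.
- **Schedule table:** marks at Visits 1, 30, 32, 34 and 35 only. Visit 29 is blank.

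Two general statements also bear on the point. Section 8.1.2 lists "Serum Beta HCG and urine pregnancy test for all menstruating females" among the data collected, without timing. Section 6.9 on unscheduled visits says "The procedures performed will be at the provider's discretion", but the procedures it refers to are those of the build-up visits plus spirometry.

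**The concern.** A dismissal rule works only if pregnancy is looked for. Build-up is a phase of daily dosing with repeated dose increases, and it has no scheduled test. A pregnancy that began then would come to light only through disclosure, history or examination, and dosing would continue until it did.

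Two features make this worse. The screening test covers girls who are menstruating at that time, so a girl who reaches menarche later has no scheduled test at all before Month 0; entry age runs from 5 to 16. And the dismissal wording is attached only to the later tests. Section 6.4 has no such rule, and the withdrawal list in 6.11 does not name pregnancy.

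What is at stake is participant safety. Sample size, endpoints and analyses are untouched.

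**Working it through.** The plan states no figure for this gap, so there is none to reproduce. The gap is built from the plan's own intervals.

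**Inputs**

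- Screening to entry challenge: up to 1 month (6.1).
- Entry challenge to first build-up visit: up to 1 month (6.4).
- Steps to 3900 mg (dose 26 in Table 3): from 1.8 mg (dose 1), 26 − 1 = 25; from 750 mg (dose 15, the highest start in Table 2), 26 − 15 = 11.
- Step length: two weeks in Table 3; at least 10 days in the text of 6.4.
- Maintenance dose reached to Month 0: 2 weeks (6.5).
- Month 0 to the challenge at Visit 30: up to 1 month (6.5, 6.6).
- 1 month taken as 4.35 weeks.

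**Formula.** Gap = windows used × 4.35 + steps × step length + 2 weeks. Up to two windows apply before Visit 29 and up to three before Visit 30.

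- 1.8 mg, two-week steps: 25 × 2 + 2 = 52.
- 1.8 mg, 10-day steps: 250/7 + 2 = 37.7.
- 750 mg, two-week steps: 11 × 2 + 2 = 24.
- 750 mg, 10-day steps: 110/7 + 2 = 17.7.

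| Start | Step | No windows used | To Visit 29, both early windows (+8.7) | To Visit 30, all three windows (+13.05) |
|---|---|---|---|---|
| 1.8 mg | 2 weeks | 52 | 60.7 | 65.05 |
| 1.8 mg | 10 days | 37.7 | 46.4 | 50.8 |
| 750 mg | 2 weeks | 24 | 32.7 | 37.05 |
| 750 mg | 10 days | 17.7 | 26.4 | 30.8 |

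All entries are in weeks. Stopping early at a highest tolerated dose shortens them; poorly tolerated doses lengthen them.

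**Against the maintenance interval.** Tests at Months 0, 12 and 24 are about 52 weeks apart. For a 1.8 mg start at two-week steps the build-up gap is equal to that (52 − 52 = 0), up to 60.7 − 52 = 8.7 weeks longer if it ends at Visit 29, or up to 65.05 − 52 = 13.05 weeks longer if it ends at Visit 30. Every 750 mg gap is shorter.

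**Against a pregnancy.** The documents give no duration. Assume nine to ten months, which is 9 × 4.35 = 39.2 to 10 × 4.35 = 43.5 weeks. The 52 to 65 week gaps exceed that range; all the 750 mg gaps fall below it.

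**Visit 29 or Visit 30.** Section 6.5 defines Month 0 as the visit two weeks after the maintenance dose is reached, with the challenge following within a month. The schedule gives Visit 29 the month-zero maintenance label. Section 6.5 also orders skin testing at Month 0, and the schedule marks that at Visit 29. So the 6.5 pregnancy test belongs at Visit 29, while the schedule marks the test only at Visit 30. Text and table disagree.

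**The case against.** The strongest reply is that the plan accepts 12 months between tests in maintenance, at the full 3900 mg dose, so a 52-week gap in build-up is in line with its own practice. That stands as to size: the gap is similar, not out of scale. A reader might infer that build-up needs closer testing because escalation is more dangerous to a fetus than maintenance. The documents do not say so, and this point does not rest on it. It rests on the exclusion, the dismissal rule and the Section 7 warning having no scheduled test behind them in this phase, when visits about every two weeks make one easy to add.

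Other controls exist: contraception (3.1) and a history and examination at each build-up visit (6.4). They lower the risk, and an advanced pregnancy might well be noticed at one of these visits. Neither is a scheduled test. Section 8.1.2 gives no timing. A reader might take 6.9 as permission to test at unscheduled visits, but pregnancy tests are not among the procedures it names, and the schedule marks none there.

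A reader might also take 65 weeks as simply the gap, or Month 0 as an ambiguous label, since 6.5 itself says that blood is "drawn at Visit 30- Month 0 DBPCFC". The definition of Month 0 and the skin-test entries support Visit 29, so on the text of 6.5 the maximum is about 61 weeks. The 65-week figure holds only if sites follow the schedule table.

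Finally, the consequence may be nil: 15 subjects are planned, and the number of menstruating girls is not given.

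**Conclusion.** The point holds. The text of 6.4 and the schedule agree that none of the 26 build-up visits has a pregnancy test, and nothing elsewhere supplies one. For a 1.8 mg start at two-week steps the gap after screening is 52 to about 61 weeks (Visit 29) or up to about 65 weeks (Visit 30). For a 750 mg start it is about 18 to 37 weeks across both step lengths. On the assumed duration, a whole pregnancy could fall between scheduled tests in the longest cases.

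These figures assume escalation to 3900 mg without repeated or delayed steps. The number of girls affected could be anywhere from 0 to 15. This is a safety-monitoring gap worth closing because closing it is cheap. It is not evidence that the plan departs far from its own testing interval, and it does not affect any endpoint or analysis.

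**What to change.** 1. Add to 6.4 and to the schedule's pregnancy-test row a urine test for females of reproductive potential, at the first build-up visit before dosing and at the existing six-weekly blood-draw visits (weeks 6 to 48, and later ones if build-up is prolonged). State that this includes girls who reach menarche after screening. Avoid wording such as menstruating at that visit, which could leave out a girl whose periods have stopped because she is pregnant.
2. State that the existing dismissal rule applies to these tests.
3. Mark the 6.5 Month 0 test at Visit 29 in the schedule, or state in 6.5 that the Visit 30 test serves.

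Urine is preferable because blood is already at its limit (6.3: "we will collect the maximum amount of blood allowable"), and the trial already uses urine tests later.

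**Effect, counting weeks from the girl's first build-up visit.** The gap from screening to first dose is at most 2 × 4.35 = 8.7 weeks, and tests are then about 6 weeks apart. The last build-up test falls at most about 6 + 2 = 8 weeks before Visit 29, or 8 + 4.35 = 12.35 weeks before Visit 30. Gaps of about 52 weeks remain in maintenance, so the longest gap in the trial falls only to that level.

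**Cost.** No new visit and no extra blood. Tests per girl: 1 + 8 = 9 for a 1.8 mg start at two-week steps; 1 + 3 = 4 (weeks 6, 12, 18) for 750 mg at two-week steps; 1 + 2 = 3 (weeks 6, 12) for 750 mg at 10-day steps; slightly more than 9 if build-up is prolonged. Without prolongation the trial total is 0 to 15 × 9 = 135. Section 7 says families are not charged for urine pregnancy tests, so the study pays. The real downside is confidentiality: parents who ask are told the results (Section 7), so more tests mean more such occasions.

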8. DATA MANAGEMENT ISSUES

8.1. Sources of Research Material:

8.1.1. Existing records:

Previous CAP-FEIA serum IgE reports will be included in each subject's record. Existing subject medical records will not otherwise be used unless records are needed to verify or clarify the severity of the original reaction to peanut ingestion.

8.1.2. Data collected during research:

- Consent and assent
- Demographic information (age, sex, ethnicity)
- History and Physical examination (including diet history, family history, past medical and past surgical history)
- Allergy skin prick testing to peanut
- Mechanistic blood draws
- Serum Beta HCG and urine pregnancy test for all menstruating females.
- Observed dosing adverse event log.
- Concomitant medication administration while on study.
- Spirometry and/or peak flow
- Double-Blinded Placebo Controlled Food Challenge (DBPCFC) (for those with confirmed CAP-FEIA serum IgE > 7 and a negative pregnancy test).

8.1.3. Home diaries:

Symptom diaries will be recorded daily by participants.

8.2. Data and Safety Monitoring Plan

This study will be reviewed regularly by a Data and Safety Review Committee (DRC). The DRC will monitor the study for progress and enrollment, toxicities, adverse events, and soundness of data. The committee will consist of Drs. [name], [name]

[name], [name] and [name]. All the members of the Data Safety Monitoring Board are affiliated with Baylor College of Medicine.

8.3. Quality Assurance

Quality Assurance (QA) Review will be conducted at least once shortly after initiation of participant recruitment, annually during the study (or more frequently if indicated), and at the end or closeout of the trial. The number of participants audited will be determined by available time and the complexity of the protocol.

The audit will include a review of source documentation to evaluate compliance for:

- Informed consent documents and procedures
- Adherence to eligibility criteria
- Protocol defined treatment
- Required baseline, on study and follow-up protocol testing
- IRB and other regulatory documents (submitted amendments, annual continuing review reports, SAEs)
- Case Report Form submissions: timelines and accuracy

Each QA review will be summarized and a final report will be sent to the PI within 30 days of the completion. The report will include a summary of findings, participant by participant case review, specific recommendations on any performance and/or shortcomings and request for corrective action, when necessary.

